1.3 Report Generation

The final statistical report will describe and justify any deviations from the original statistical plan described herein. Analyses will be performed using SAS 9.4 software or most current version of R. No adjustments for multiple comparisons will be made. Any analyses requiring CFFNPR data will be performed after the study close-out. The timing of these analyses will depend on availability of the Registry data containing relevant study participant information. Any tables or figures requiring such data are noted with an asterisk in the table and figure shells that follow. All programs used to produce this report will be documented, tested, and archived and all tables, figures and listings will be validated before considered final.

1.4 Definition of the Analysis Populations

Enrollment and screening summaries will be generated using all screened participants. All compliance and safety analyses will be performed using an intent-to-treat (ITT) population, defined as all subjects randomized at Visit 2. The ITT population will also be used to generate all NERR primary efficacy analyses. The primary ERR analyses will be performed using per-protocol population (PP), defined as subjects in the ITT population who have no protocol violations.

2. Results

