5.2 Secondary Endpoints

Efficacy

- Absolute change in CRISS from Visit 1 (Baseline) to Visit 3
- Proportion of patients retreated for pulmonary exacerbation within 30 days following scheduled completion of IV antibiotics as collected in the CFFNPR

- Time (days) to next pulmonary exacerbation following scheduled completion of IV antibiotics as collected in the CFFNPR
- Relative change in FEV₁ (liters) from Visit 1 (Baseline) to Visit 3
- Absolute change in weight (kg) from Visit 1 (Baseline) to Visit 3

Safety

- Incidence of adverse events, including clinically significant abnormal lab values
- Retreatment of pulmonary exacerbation prior to Visit 3

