15 STATISTICAL METHODS AND CONSIDERATIONS

A detailed Statistical Analysis Plan (SAP) will be written that will describe all analyses that will be generated for this study. All analyses will be performed using SAS[®] (SAS Institute, Inc., Cary, NC, USA) or R (R Foundation for Statistical Computing, Vienna, Austria). The SAP will contain any modifications to the analysis plan described below.

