15.4 Analysis of Secondary Endpoints

Descriptive analyses and graphical displays will be used to summarize all secondary endpoints, including changes from baseline in continuous endpoints and rates over the follow-up period for event based endpoints. The ITT and PP populations will be used for all secondary analyses.

All reported SAEs and AEs will be coded using MedDRA and grouped by body system. (S)AEs will be tabulated by treatment durations within ERR and NERR groups using standard coding terms sorted by body system. The incidence of AEs (including emergent abnormal lab values collected for clinical care) in each treatment duration arm will be tabulated by seriousness, severity, and relationship to arm. If an AE is reported more than once during the study period for a given subject, the greatest severity and the worst-case relationship will be presented in tables. The number of (S)AEs will be summarized by treatment duration arms within ERR and NERR groups as follows: (i) The proportion of subjects with at least one (S)AE, (ii) The average number of (S)AEs per patient, and (iii) The rate of (S)AEs per patient month of follow-up. Histograms showing the frequency of the number of (S)AEs in each treatment duration arm will be included. Rates of (S)AEs by System Organ Class (SOC) will be presented by treatment duration arm. Poisson regression modeling will be used to derive rate ratios and 95% confidence

intervals for each SOC. The rate ratios will be compared using a two-sided 0.05 level test for Poisson count data.

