ERR subjects [$\geq 8\%$ predicted improvement in FEV₁ from Baseline (Visit 1) to Visit 2 and CRISS reduction of ≥ 11 points from Baseline (Visit 1) to Visit 2] will be randomized 1:1 to either 10 days or 14 days total IV antibiotic treatment duration. Remaining (NERR) subjects will be randomized 1:1 to receive either 14 or 21 days total IV antibiotic treatment duration. All subjects will be evaluated again at Visit 3, 14 days following scheduled completion of IV antibiotic treatment. Dependent on the treatment arm, subjects will be on study from 24 to 35 days.

The primary objective of this study is to evaluate the efficacy and safety of differing durations of IV antibiotic treatment for CF pulmonary exacerbations.

ERR Group: To determine if 10 days of IV antibiotic treatment (ERR-10) is as safe as and not clinically inferior (in terms of lung function response) to 14 days of IV antibiotic treatment (ERR-14) among subjects meeting the ERR threshold at Visit 2.

NERR Group: To determine if 21 days of IV antibiotic treatment (NERR-21) is clinically superior (in terms of lung function response) and safe, compared to 14 days of IV antibiotic treatment (NERR-14) among subjects not meeting the ERR threshold at Visit 2.

The secondary objectives are to:

- Evaluate efficacy of differing IV antibiotic treatment durations on other clinical outcomes such as weight, respiratory symptoms, and subsequent IV antibiotic treatments for pulmonary exacerbation.

- Determine the feasibility, uptake and adherence to a standardized protocol of antibiotic selection.

Other objectives are to:

- Provide a study platform for ancillary studies of PEx treatment in adults with CF, including investigations into respiratory microbiome, health economics, and systemic inflammation.
- Establish a biorepository of CF serum and sputum samples before, during and after treatment for an adult PEx for use by the CF research community. Interim DSMB Reviews

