2.3 Adverse Events

All reported SAEs and AEs are coded using MedDRA and grouped by body system. (S)AEs are tabulated by treatment durations within ERR and NERR groups using standard coding terms sorted by body system. The incidence of AEs (including emergent abnormal lab values collected for clinical care) in each treatment duration arm is tabulated by seriousness, severity, and relationship to arm. If an AE is reported more than once during the study period for a given subject, the greatest severity and the worst-case relationship is presented in tables. The number of (S)AEs is summarized by treatment duration arms within ERR and NERR groups as follows: (i) The proportion of subjects with at least one (S)AE, (ii) The average number of (S)AEs per patient, and (iii) The rate of (S)AEs per patient week of follow-up. Histograms showing the frequency of the number of (S)AEs in each treatment duration arm are included. Rates of (S)AEs by System Organ Class (SOC) are presented by treatment duration arm. Poisson regression modeling is used to derive rate ratios and 95% confidence intervals for each SOC. The rate ratios is compared using a two-sided 0.05 level test for Poisson count data.

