2.4 Other Safety Measures

Summaries of proportions of participants experiencing any elevated and clinically significant BUN or creatinine findings between Visit 1 and Visit 3 are provided.

Also summarized are proportions of participants retreated with IV antibiotics. Retreatment is defined as any additional IV antibiotics administered 3 or more days after the stop date of the initial IV antibiotic treatment for pulmonary exacerbation and prior to Visit 3 (e.g. rescue treatment or treatment of the new pulmonary exacerbation).

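### The ERR objective claims 10 days is 'as safe as' 14, but no planned safety analysis is set up to support that; retreatment before Visit 3 needs a risk difference with a 95% CI

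*SAP*

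**What the plan says.** **Objective.** The ERR part of the primary objective in SAP 1.1, matched in Protocol 3.1, reads: "To determine if 10 days of IV antibiotic treatment (ERR-10) is as safe as and not clinically inferior" to 14 days. The qualifier about lung function belongs to the non-inferiority half, so safety is a claim of its own.

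**Endpoints.** Protocol 5.2 lists adverse events and "Retreatment of pulmonary exacerbation prior to Visit 3" as secondary safety endpoints.

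**Population.** SAP 1.4: "All compliance and safety analyses will be performed using an intent-to-treat (ITT) population". Protocol 15.4, the section that also sets out the adverse event analysis: "The ITT and PP populations will be used for all secondary analyses". SAP 2.5 repeats only the primary efficacy analysis in the other population.

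**Methods.**
- Adverse events (SAP 2.3): rate ratios with 95% CIs by System Organ Class, "compared using a two-sided 0.05 level test for Poisson count data".
- Retreatment before Visit 3 (SAP 2.4): "Also summarized are proportions of participants retreated with IV antibiotics". The text names no difference, test or interval.
- Registry retreatment within 30 days (SAP 2.6): a difference in proportions, estimated and tested two-sided.
- Time to next exacerbation (SAP 2.7): Cox hazard ratio with a 95% CI.

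Neither document gives a safety margin, a power figure for safety, or a rule for concluding that the shorter course is as safe.

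**The concern.** A claim of equal safety is a no-difference claim. The plan knows how to handle one: for FEV₁ in the ERR group it sets a 3.5-point margin and reads the 95% CI against it. The safety half of the same sentence has nothing comparable. Where safety is tested, the null hypothesis is no difference, and failing to reject that null says little when events are few.

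The gap matters most for retreatment before Visit 3. Protocol 2.1 names early relapse as the risk of too short a course, and this endpoint is the closest measure of it collected in the study itself. The registry endpoints cover similar ground, but Protocol 6.2 requires registry enrolment at US sites only, and Protocol 9.3.2 foresees Canadian sites. If two similar percentages are tabulated without an interval, a reader may take the safety objective as met without seeing how large an excess the data leave open.

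**Working it through.** **1. The plan's own figure.** Protocol 15.7: 155 completers per ERR arm, SD 9.0, margin 3.5, true difference zero, two-sided 0.05.
- SE = 9.0 × √(2/155) = 1.022.
- Power = Φ(3.5/1.022 − 1.96) = Φ(1.46) = 92.8%, against the stated 93%.
- CI half-width = 1.96 × 1.022 = 2.0, as stated.

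These figures reproduce, but they concern FEV₁ only.

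**2. ERR numbers in ITT.**
- Minimum: 310 completers with 4% drop-out after Visit 2 gives 310/0.96 = 323 randomised, or 162 per arm.
- Expected: one third of 1236 randomised is 412, or 206 per arm.

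**3. Precision for retreatment before Visit 3.** The documents give no rate, so 5%, 10% and 15% are assumptions. With equal rates p in both arms, the half-width of the 95% CI for the risk difference is 1.96 × √(2p(1−p)/n).

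| Assumed rate | 162 per arm | 206 per arm |
|---|---|---|
| 5% | 4.7 points | 4.2 points |
| 10% | 6.5 points | 5.8 points |
| 15% | 7.8 points | 6.9 points |

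Example: p = 0.10, n = 206 gives 1.96 × √(0.18/206) = 1.96 × 0.0296 = 5.8 points. If the observed rates were identical, the interval would still leave open an excess of up to 5.8 points in ERR-10. A bare tabulation does not show this.

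**4. Would PP help for retreatment?** Protocol 8.2 says that no further antibiotics should follow the assigned course, apart from stated exceptions. Protocol 13 counts a prohibited concomitant medication as a violation. Protocol 15.1 and SAP 1.4 remove anyone with a violation from PP. Read together, a retreated subject may leave PP because of the retreatment, so PP could delete the events being counted.

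**5. Direction of dilution in ITT.** Protocol 2.1 attaches relapse to a short course, and drug toxicity and catheter complications to a long one. Non-adherence to assigned duration pulls the arms together. For relapse that can hide a harm of ERR-10; for toxicity it can hide an advantage.

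**The case against.** The strongest case on the other side is that the plan already gives intervals. System Organ Class rate ratios carry 95% CIs (SAP 2.3), and so does the hazard ratio for time to next exacerbation (SAP 2.7). Low precision would show there as wide intervals. The 30-day registry endpoint starts at scheduled completion and so spans the two weeks to Visit 3. ITT is a usual safety population. Neither document says that p > 0.05 would be read as equal safety. SAP 1.3 refers to table shells that are not in the supplied text, and these might contain interval columns. All of this stands, and it makes the point minor. It does not supply a basis for concluding equal safety, and it does not give the SAP text an estimate for retreatment before Visit 3.

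A reader might infer three stronger things that the documents do not support:
- **That SAP 1.4 breaches the protocol and a PP repeat is the remedy.** Protocol 15 says "The SAP will contain any modifications to the analysis plan described below", so the difference is permitted; it is simply not flagged. For retreatment, PP may remove the events.
- **That the trial would probably miss a real excess in its significance test.** With 206 per arm and assumed ERR-14 rates of 2% to 15%, a two-sided 0.05 test would miss a 5-point excess 31% to 73% of the time. But no test of this endpoint is planned, so the figure describes no analysis in the SAP.
- **That ITT dilution generally favours a finding of equal safety.** This holds for relapse but not for toxicity.

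**Conclusion.** The point holds at minor severity. The ERR primary objective makes an equal-safety claim for which the plan has difference tests, some confidence intervals and no rule. The endpoint nearest to the named risk of a short course is only tabulated. The half-width of about 4 to 8 percentage points rests on assumed retreatment rates of 5% to 15%, equal rates in the two arms, and 162 to 206 subjects per arm; it illustrates the available precision and predicts nothing about the result. The difference between SAP 1.4 and Protocol 15.4 on the safety population is an unflagged inconsistency that needs reconciling, and it is no reason to move the main safety analysis out of ITT.

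**What to change.** 1. **SAP 2.4:** report the ERR-10 minus ERR-14 risk difference for retreatment before Visit 3 with a 95% CI in ITT.
2. **SAP 2.3, 2.4 and 2.6:** say that the safety conclusion rests on the confidence intervals, stated as the largest excess not excluded, and that p > 0.05 is not evidence of equal safety. Alternatively, word the safety part of the ERR objective in Protocol 3.1 and SAP 1.1 as estimating the difference.
3. **SAP 1.4 and Protocol 15.4:** reconcile the safety population, or record the change and the reason for it. Keep ITT as the main safety set. Do not rely on PP for retreatment. Any analysis based on adherence or on duration actually received should be labelled supportive.

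The cost is one added estimate from data already collected, some wording (with a protocol edit if the objective is reworded), and a safety statement that will sound less favourable than 'as safe as'.

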2.1 Enrollment and Screen Failures

The cumulative enrollment of participants randomized into the study is graphically summarized. The number of participants screened, eligible, randomized, withdrawn, and completing the study is summarized by treatment duration arm and site within ERR and NERR groups.

The un-randomized participants are categorized as screen failures, those discontinuing the study before randomization, or eligible but not randomized. Reasons for screen failures, study discontinuations, and decision to not randomize are given. The screen failure reasons are summarized for all screening attempts.

Participants who are deemed eligible at Visit 1 but are not assessed at Visit 2 are further summarized by age group, admission FEV₁, and IV antibiotic location (home vs hospital).

Participant disposition figure detailing enrollment, treatment allocation, follow-up, and analyses populations is provided.

2.2 Withdrawals, Treatment Duration Compliance, and Prohibited Antibiotic Utilization

The number of participants who withdrew early from the study is tabulated by treatment duration arm within ERR and NERR groups. The reason for withdrawal is also listed. Withdrawals are further summarized by age group, admission FEV₁, and IV antibiotic location (home vs hospital).

Treatment duration adherence is summarized descriptively by treatment duration arm within ERR and NERR groups. Also included are descriptive summaries of prohibited antibiotic use and unplanned use of corticosteroids.

2.2 Demographics and Baseline Characteristics

Treatment duration arms within ERR and NERR groups are described and compared with respect to Baseline demographic and clinical characteristics including age, sex, CFTR genotype, race, height, weight, and all randomization strata. For all analyses, Baseline clinical characteristics are defined as measurements obtained at Visit 1.

2.3 Adverse Events

All reported SAEs and AEs are coded using MedDRA and grouped by body system. (S)AEs are tabulated by treatment durations within ERR and NERR groups using standard coding terms sorted by body system. The incidence of AEs (including emergent abnormal lab values collected for clinical care) in each treatment duration arm is tabulated by seriousness, severity, and relationship to arm. If an AE is reported more than once during the study period for a given subject, the greatest severity and the worst-case relationship is presented in tables. The number of (S)AEs is summarized by treatment duration arms within ERR and NERR groups as follows: (i) The proportion of subjects with at least one (S)AE, (ii) The average number of (S)AEs per patient, and (iii) The rate of (S)AEs per patient week of follow-up. Histograms showing the frequency of the number of (S)AEs in each treatment duration arm are included. Rates of (S)AEs by System Organ Class (SOC) are presented by treatment duration arm. Poisson regression modeling is used to derive rate ratios and 95% confidence intervals for each SOC. The rate ratios is compared using a two-sided 0.05 level test for Poisson count data.

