2.1 Risk / Benefit Assessment

Treatment-Associated Risks:

This is an interventional study that will dictate the duration of IV antibiotics for the treatment of pulmonary exacerbation. There can be risks associated with the randomization as patients might be allocated to a duration of antibiotic therapy that may be too short or too long. The potential risk of an insufficient duration of antibiotics is an early relapse of the exacerbation, although surveys of CF clinicians reveal that a majority consider any new treatment for an exacerbation, at any time after the previous treatment, to be a new event rather than a relapse. The potential risks of an excess duration of antibiotics include unnecessary cost as well as the potential for injury attributed to the treatment, specifically drug toxicity (e.g., antibiotic-associated nephrotoxicity, ototoxicity, neurotoxicity, and/or vestibular toxicity, *C. difficile* colitis due to broad spectrum

antibiotic use) or a complication related to the indwelling IV catheter (e.g., thrombus). Clinicians are keenly aware of these potential complications as part of standard therapy and monitor these risks routinely. Generally, intravenous antibiotics used to treat acute pulmonary exacerbation in CF are all well tolerated, and CF patients have extensive experience receiving repeated courses of intravenous antibiotics for acute pulmonary exacerbation.

It is noted that the duration of antibiotics will be 10, 14 or 21 days, which are consistent with current durations used to treat patients (CFFNPR data). Of note, 50% of patients will be randomized to 14 days of IV antibiotics, which is the most frequently used duration (CFFNPR data) and the most frequently reported duration by CF clinicians (survey data, not published). In addition, the randomization is based upon the initial response to treatment such that the duration of antibiotics is even more likely to be consistent with current treatment practices [i.e., patients with a robust response will tend to get a shorter duration (10 vs 14 days) while those with a more sluggish response will tend to get a longer duration (14 vs. 21 days)]. This randomization allocation should mitigate the risks of inappropriately short or long durations as they will be tied to the initial patient response and are consistent with common practice among CF clinicians.

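### The harms that the protocol attributes to excess antibiotic duration are never compared between arms as a group; the only adverse-event test is one unadjusted rate ratio per System Organ Class

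*SAP*

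**What the plan says.** **Objective.** SAP 1.1 states the NERR aim as: "To determine if 21 days of IV antibiotic treatment (NERR-21) is clinically superior (in terms of lung function response) and safe", compared with 14 days. The ERR aim is that 10 days be as safe as 14. Protocol 3.1 agrees on both.

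**Harms named in advance.** Protocol 2.1 says: "The potential risks of an excess duration of antibiotics include unnecessary cost as well as the potential for injury attributed to the treatment". It then lists "antibiotic-associated nephrotoxicity, ototoxicity, neurotoxicity, and/or vestibular toxicity", adds C. difficile colitis, and ends with a "complication related to the indwelling IV catheter (e.g., thrombus"). That makes six harms.

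**Tests.** SAP 2.3 gives one inferential adverse-event analysis: "Poisson regression modeling is used to derive rate ratios and 95% confidence intervals for each SOC", followed by "The rate ratios is compared using a two-sided 0.05 level test for Poisson count data". Protocol 15.4 matches. SAP 1.3 adds: "No adjustments for multiple comparisons will be made".

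**Other safety reporting.** SAP 2.3 also tabulates events by coding term, seriousness, severity and relationship to arm. It summarises, by arm, the proportion of subjects with any event, the mean number per patient and the rate per patient-week. SAP 2.4 summarises clinically significant BUN or creatinine findings and IV retreatment. No test is stated for any of these. No grouped endpoint, toxicity term list, safety margin, expected toxicity rate or safety power appears in either document.

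**The concern.** The harms that motivate a shorter course are few, specific and listed in advance, and they affect different body systems. A test within each SOC separates them from one another and pools each with whatever unrelated events share its SOC. The result is a set of imprecise rate ratios, each tested at 0.05 without adjustment, and none addresses the question posed in Protocol 2.1.

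At stake is the safety half of the primary objective. Protocol 15.7 sets the 2.5-point FEV₁ target as what would justify the added burden and possible toxicity of 21 days. The benefit side of that trade-off has a stated power and confidence-interval width. The toxicity side has no analysis aimed at it.

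**Working it through.** **1. The plan's own figures.** These are for efficacy only (Protocol 15.7). With SD 9, power = Φ(δ / (9·√(2/n)) − 1.96).
- NERR, δ = 2.5, n = 285 per arm: 91.2% (stated 91%).
- ERR, margin 3.5, n = 155 per arm: 92.8% (stated 93%).
- CI half-widths, 1.96·9·√(2/n): 1.48 and 2.00 (stated 1.5 and 2).

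These reproduce. There is no safety figure to reproduce.

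**2. Inputs.**
- n per NERR arm: 285 (Protocol 15.7 minimum of completers) to 412. The upper value is 1236 expected randomised × 2/3 NERR ÷ 2. Safety uses all randomised subjects (SAP 1.4).
- Assumed, because the documents give no rates: each harm 0.5%, 1% or 2% in the shorter arm; ratio 2 or 1.5; unrelated events in the same SOC 0%, 2% or 5%.
- Assumed coding: five separate harms, with hearing and balance toxicity counted as one because they may share an SOC. The documents do not give the coding.

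**3. Formulas.** With harm rate t and unrelated rate b, the SOC rate is 1 − (1−t)(1−b) and the group rate is 1 − (1−t)⁵. Power = Φ[(|p₂−p₁| − 1.96·SE₀)/SE₁], where SE₀ = √(2p̄(1−p̄)/n) and SE₁ = √((p₁(1−p₁)+p₂(1−p₂))/n). The chance that at least one of five SOCs is significant is 1 − (1−power)⁵, taking them as independent.

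Example, 1% v 2%, b = 5%, n = 412:
- One SOC: 5.95% v 6.90%. (0.0095 − 1.96 × 0.0171)/0.0171 = −1.40, so 8%.
- Group: 4.90% v 9.61%. (0.0471 − 1.96 × 0.0181)/0.0180 = 0.65, so 74%.

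**4. Results, each harm doubling.** The SOC columns give b = 0% / 2% / 5%.

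| Harm rate | n per arm | One SOC | Any of five SOCs | Five-harm group |
|---|---|---|---|---|
| 0.5% | 285 | 10 / 6 / 4% | 42 / 25 / 20% | 34% |
| 0.5% | 412 | 13 / 6 / 5% | 50 / 28 / 22% | 46% |
| 1% | 285 | 16 / 9 / 7% | 59 / 39 / 29% | 58% |
| 1% | 412 | 22 / 12 / 8% | 71 / 46 / 34% | 74% |
| 2% | 285 | 29 / 19 / 13% | 82 / 65 / 51% | 86% |
| 2% | 412 | 39 / 25 / 17% | 92 / 77 / 61% | 96% |

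With no true difference, five independent SOC tests give a chance excess in the longer arm 1 − 0.975⁵ = 12% of the time (23% in either direction). One grouped test gives 2.5% (5%).

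**5. Ratio 1.5, harms 1%–2%.** The group has 22%–52% power across 285–412 per arm.

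**6. Check with the planned type of test.** A simulated Poisson test without a follow-up offset, 1% v 2%, b = 5%, gives 7% (285) and 8% (412) for one SOC. All six harms grouped give 67% and 83%.

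**7. Follow-up length.** Adverse events run from Visit 2 to Visit 3 (Protocol 11.1). Taking Visit 2 at day 8.5, that is 28 − 8.5 = 19.5 days in NERR-14 and 35 − 8.5 = 26.5 in NERR-21; in ERR it is 15.5 v 19.5.
- Raw risks: with equal hazards and 4.9% in NERR-14, NERR-21 shows 1 − 0.951^(26.5/19.5) = 6.6%. The chance of a significant excess from follow-up length alone is 18% (412) or 14% (285).
- Rates per unit time: a doubled cumulative risk becomes a rate ratio of 2 × 19.5/26.5 = 1.47. The six-harm Poisson power at 285 per arm, 1% doubling, falls from 67% to 25%.

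SAP 2.3 reports rates per patient-week but does not say whether the regression uses follow-up time as an offset.

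**The case against.** **The size depends on assumed inputs.** This stands. Unrelated background matters most. At 0% background and 1% v 2%, looking for any significant SOC gives 71% against 74% for the group at 412 per arm, and 59% against 58% at 285; at 0.5% v 1% it does better than the group. Protocol 11.1 opens by confining adverse events to those related to participation or procedures, or otherwise judged significant, which could keep background low. Its next sentence is broader, so the level remains open. Even then, the any-SOC reading carries the higher chance-finding rate shown above.

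**A reader might infer that a doubling of toxicity would usually be missed.** The documents do not support that. They give no rates, and at 2% v 4% with 412 per arm at least one of five SOCs is significant 61% of the time even with 5% background.

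**A reader might infer that the SOC split is what leaves safety underpowered.** Rarity and sample size matter as much. The group itself reaches only 58% at 285 per arm for 1% v 2%. In ERR, on the same assumptions, it reaches 36% (155 per arm) to 45% (206 per arm, from 1236 ÷ 3 ÷ 2).

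**A reader might infer that the named harms go unreported.** They do not. Coding-term tables, overall proportions and a separate BUN/creatinine summary exist, and SAP 1.2 gives the DMC safety by arm. What is missing is a comparison of the named harms together.

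**A grouped raw risk could unfairly count against the longer arm.** This also stands, because of the difference in follow-up, and it shapes the fix.

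**Conclusion.** The point holds as a gap in the analysis plan. Safety is part of the primary objective and the protocol names the harms of excess duration, but no planned comparison asks whether those harms taken together differ by arm. For a doubling of harms of 0.5%–2% with 0%–5% background, a single SOC test has about 4%–39% power and a five-harm group about 34%–96%, at 285–412 per arm. These ranges rest on assumed rates, assumed SOC coding and independence between harms. The advantage over the any-SOC reading is large only if unrelated events are common in those SOCs. At a ratio of 1.5 neither approach is adequate. This is a cheap improvement. The documents do not show that the planned analysis would fail to detect a safety problem.

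**What to change.** In SAP 2.3, pre-specify one grouped comparison:

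- Fix a MedDRA term list for the six harms named in Protocol 2.1. It should be agreed before by-arm adverse-event data are seen by those choosing the terms. SAP 1.2 gives the study biostatisticians the closed safety reports, so the choice should rest with people who do not receive them.
- Count each patient once if any listed event starts after randomisation. Report NERR-21 v NERR-14 and ERR-14 v ERR-10 as a risk difference with 95% CI, with each component shown.
- Follow-up to Visit 3 is about a week longer in NERR-21 and about 4 days longer in ERR-14. So also report the result over a common window from randomisation, or as an exposure-adjusted rate. State that the two answer different questions: total harm under each assignment, and harm over equal time.
- Label the per-SOC rate ratios as descriptive.

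The cost is one term list and one table from events already MedDRA-coded, with no new data collection. The downsides are that the group pools harms of unequal severity and remains imprecise if events are rare, so the interval should carry the interpretation.

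### The per-SOC adverse-event rate ratios rest on a plain Poisson variance, so their 95% CIs are too narrow and their 0.05 tests too liberal wherever events cluster within patients

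*SAP*

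**What the plan says.** SAP 2.3 (Adverse Events) sets out the between-arm comparison within the ERR and NERR groups: "Poisson regression modeling is used to derive rate ratios and 95% confidence intervals for each SOC". It continues: "The rate ratios is compared using a two-sided 0.05 level test for Poisson count data". Protocol 15.4 has the same plan: "Poisson regression modeling will be used to derive rate ratios and 95% confidence" intervals for each SOC, and "The rate ratios will be compared using a two-sided 0.05 level test for Poisson count data". Neither section mentions overdispersion, a scale parameter, robust standard errors, a negative binomial model or a patient-level effect.

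The descriptive summaries in SAP 2.3 count events. After the proportion of subjects with any event, they list "ii) The average number of (S)AEs per patient, and (iii) The rate of (S)AEs per patient week of follow-up". The SAP also plans to show how counts vary between patients: "Histograms showing the frequency of the number of (S)AEs in each treatment duration arm are included". For an AE reported more than once by the same subject, "the greatest severity and the worst-case relationship is presented in tables". That rule governs table display; it does not say what enters the model.

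On the population, SAP 1.4 states: "All compliance and safety analyses will be performed using an intent-to-treat (ITT) population, defined as all subjects randomized at Visit 2". Protocol 8.1 sets minimum arm sizes of 155 (ERR) and 285 (NERR). SAP 1.3 rules out any adjustment for multiple comparisons.

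**The concern.** A Poisson model takes the variance of a count to equal its mean. That is doubtful for adverse-event counts when one patient can supply several related events. Protocol 11.1 defines AEs at the level of signs, symptoms and clinically significant laboratory values, so a single clinical episode could be recorded as more than one term in the same SOC. If so, the counts vary more than Poisson, and the standard error of the log rate ratio is too small by the square root of the dispersion.

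The comparison has some weight. Safety is part of the primary objective in both response groups, and the per-SOC rate ratios are the only formal between-arm AE tests that SAP 2.3 describes. An interval that is too narrow can suggest harm from either duration where there is none, or give more reassurance than the data support.

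**Working it through.** **Inputs from the documents.** Two-sided level 0.05 (SAP 2.3, Protocol 15.4). Arms of 155 (ERR) and 285 (NERR) (Protocol 8.1). AE window from Visit 2 to Visit 3 (Protocol 11.1), with Visit 2 on Day 7–10 and Visit 3 14 days after scheduled end of IV treatment. Taking Visit 2 at Day 8.5, the windows are:
- ERR-10: 24 − 8.5 = 15.5 days; ERR-14: 28 − 8.5 = 19.5 days (about 2.2 and 2.8 weeks).
- NERR-14: 28 − 8.5 = 19.5 days; NERR-21: 35 − 8.5 = 26.5 days.

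**Assumed, because the documents give no figure.** Event rate per SOC and degree of clustering. Both are varied below.

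**Step 1: level as a function of dispersion.** Let φ be the variance divided by the mean of per-patient counts. With event totals A and B, the Poisson variance of the log rate ratio is 1/A + 1/B; the true variance is about φ(1/A + 1/B). Hence

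true level = 2 × [1 − Φ(1.96/√φ)].

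| φ | 1.96/√φ | True level | Factor by which the CI should widen (√φ) |
|---|---|---|---|
| 1.0 | 1.960 | 0.050 | 1.00 |
| 1.2 | 1.789 | 0.074 | 1.10 |
| 1.5 | 1.600 | 0.110 | 1.22 |
| 2.0 | 1.386 | 0.166 | 1.41 |

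The plan's 0.05 is reproduced at φ = 1, that is, when counts are truly Poisson.

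**Step 2: what clustering implies for φ.** Suppose episodes are Poisson and each yields 1 + Poisson(m) terms in the SOC. Then φ = (1 + m) + m/(1 + m), whatever the episode rate. For m = 0.5: 1.5 + 0.5/1.5 = 1.83, 1.96/√1.83 = 1.45, level 0.148. For m = 0.1, 0.25 and 1.0, φ is 1.19, 1.45 and 2.5, and the level is 0.073, 0.104 and 0.215.

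**Step 3: simulation under no rate difference.** 10,000 trials per setting under this mechanism, with the windows above and a Wald test of the log rate ratio with a person-time denominator. Rejection rates of the plain Poisson test:

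| Group | Episodes per patient (shorter arm) | m = 0.1 | m = 0.25 | m = 0.5 | m = 1.0 |
|---|---|---|---|---|---|
| ERR, 155 per arm | 0.25 | 7.0% | 10.2% | 15.7% | 21.5% |
| ERR | 0.05 | 5.3% | 8.2% | 13.3% | 20.3% |
| ERR | 0.02 | 1.8% | 3.7% | 6.8% | 13.4% |
| NERR, 285 per arm | 0.25 | 7.5% | 10.0% | 14.8% | 22.0% |
| NERR | 0.05 | 6.1% | 9.8% | 14.0% | 21.2% |
| NERR | 0.02 | 4.5% | 7.3% | 11.8% | 19.0% |
| NERR | 0.01 | 1.0% | 2.4% | 5.9% | 12.4% |

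With patient-level robust variance, the rows at 0.05 and 0.25 reject in 4.4% to 5.6% of trials. In the rows at 0.01 and 0.02 the robust test rejects in 0.9% to 5.0%, so it too is often conservative when events are few.

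**Step 4: a different clustering mechanism.** If patients differ in susceptibility (gamma frailty, variance 1 to 4, assumed), φ = 1 + rate × frailty variance, so inflation fades as the SOC becomes rarer. The simulated Poisson level is 13–31% at 0.6 events per patient, 9–21% at 0.3, 6–10% at 0.1, about 4–6.5% at 0.05, and below 5% at 0.02.

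**Step 5: the other counting unit.** If each patient counts at most once per SOC, the count is binary and its variance is below its mean. With equal follow-up and rates from 0.02 to 0.6, the Poisson test then rejects in 0.4% to 4.1% of null trials.

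**The case against.** The best case for the plan has four parts.

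- **Clustering is not shown.** No SOC rate or dispersion is given, and no text says that a relapse is recorded as several respiratory terms instead of one diagnosis. Protocol 11.1 also ties AEs to study participation, study procedures or the investigator's judgement of significance, and the window is only about two to four weeks. Many SOCs may have few events. This stands: the sizes above are conditional, and with weak clustering in a very sparse SOC the test is near nominal or conservative.
- **The counting unit of the model is not stated.** Counting once per patient per SOC would reverse the direction. This stands too, although the rates and averages in SAP 2.3 point to events.
- **Little hangs on these tests.** AE incidence is a secondary endpoint (Protocol 5.2), no decision rule or margin uses a per-SOC p-value, and unadjusted tests over many SOCs will produce chance signals even at an exact 5%. This limits the importance of the point. It does not justify intervals that miss their stated coverage.
- **Other summaries are robust or revealing.** The proportion with at least one event is immune to clustering, and the histograms could expose overdispersion. But no test of that proportion is described, and nothing links the histograms to the choice of variance.

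A reader might infer that every SOC interval is too narrow, or that the trial will produce false safety signals across many SOCs. The documents support neither: both need event rates and clustering that they do not report.

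**Conclusion.** The point holds conditionally. The plan specifies a Poisson variance for events that can recur within a patient and makes no provision for clustering. Where clustering exists in a reasonably frequent SOC, the CIs are too narrow and the test too liberal: 7%, 11% and 17% true level at dispersion 1.2, 1.5 and 2.0. For 0.05 to 0.25 episodes per patient and 0.1 to 1.0 extra terms per episode, the simulated range is about 5% to 22% for both arm sizes. At 0.01 to 0.02 episodes per patient, weak clustering leaves the test near nominal or conservative, while strong clustering can still inflate it. These rates and clustering strengths are assumptions.

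It would go too far to conclude that the safety part of the primary objective fails or that the efficacy result is in doubt. The FEV₁ analysis does not use this model, and no stated decision depends on it. This is a cheap improvement to a secondary safety analysis.

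**What to change.** In SAP 2.3:

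1. State that the per-SOC model counts events, and say how repeats of the same AE in one subject are counted.
2. Keep the log-linear rate model and write out the log person-time offset.
3. Base the rate-ratio CIs and the two-sided 0.05 tests on robust (sandwich) standard errors clustered on patient.
4. For SOCs with very few events, use an exact test on patients with at least one event, and give the event-number threshold for switching before the data are seen.

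Protocol 15 lets the SAP modify the analyses it describes, so the change can be made in the SAP. It should be made before database lock.

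The cost is one option in the same SAS or R procedure plus a few lines of text. CIs become somewhat wider where events cluster, by a factor of √φ (1.22 at dispersion 1.5). Without clustering, and outside very sparse SOCs, the results are nearly the same as under plain Poisson.
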